7.9.1 Acceptable Concomitant Medications

All treatments that the investigator considers necessary for a subject's welfare may be administered at the discretion of the investigator in keeping with the community standards of medical care. All concomitant medication will be recorded in Epic including all prescription, over-the-counter (OTC), herbal supplements, and IV medications and fluids.

All concomitant medications received within 28 days before the first dose of trial treatment and 30 days after the last dose of trial treatment should be recorded. Concomitant medications administered after 30 days after the last dose of trial treatment should be recorded for SAEs and ECIs as defined in Section 7.2.

7.9.2 Prohibited Concomitant Medications and Therapies

Subjects are prohibited from receiving the following therapies during the Screening and Treatment Phase (including retreatment for post-complete response relapse) of this trial:

- Antineoplastic systemic chemotherapy or biological therapy not specified in this protocol

- Immunotherapy not specified in this protocol
- Chemotherapy not specified in this protocol
- Live vaccines within 30 days prior to the first dose of trial treatment and while participating in the trial. Examples of live vaccines include, but are not limited to, the following: measles, mumps, rubella, varicella/zoster, yellow fever, rabies, BCG, and typhoid vaccine.
- All herbal and natural supplement that are being used will be recorded at all clinic visits. Natural therapies and herbal supplements may stimulant or suppress subjects immune system. Immune suppressants may reduce the efficacy of pembrolizumab and their concomitant use may potentially increase the risk of infections. Concomitant use of immune stimulants may potentially increase the risk of adverse auto-immune responses. Concomitant use of the natural therapies and herbal supplements in Table 7 below are prohibited
- Emerging data suggests that marijuana can affect response rates. The use of marijuana and marijuana derived products are allowed in this study. Subjects will be made aware (in the consent form) of the potential risks of using marijuana while on the study.

Table 7 Prohibited Concomitant Natural Therapies and Herbal Supplements

Name of herbal supplement	
Immune stimulating agents	
1. Coriolus Mushroom/DHEA	23. European mistletoe
2. 7-keto-DHEA	24. Fo-Ti Root
3. Echinacea*	25. Ginseng, panax and siberian
4. European mandrake	26. Glossy Privet (ligustrum)
5. European mistletoe	27. Greater Celandine
6. Fo-Ti Root	28. Jiaogulan
7. Ginseng, panax and siberian	29. Larch Arabinogalactan
8. Glossy Privet (ligustrum)	30. Lycium
9. Greater Celandine	31. Melatonin
10. Jiaogulan	32. MGN-3
11. Larch Arabinogalactan	33. Podophyllum
12. Lycium	34. Pokeweed
13. Melatonin	35. Pycnogenol
14. MGN-3	36. Quillaia
15. Podophyllum	37. Reishi Mushroom (gandoderma)
16. Pokeweed	38. Shitake Mushroom
17. Pycnogenol	39. Sweet Annie
18. Coriolus Mushroom	40. Terminalia chebula
19. DHEA	41. Thunder god vine
20. 7-keto-DHEA	42. Wild indigo
21. Echinacea*	43. Zinc
22. European mandrake	Note: *Can be immune suppressing also
Immune suppressing agents	
1. Bitter Melon	8. Fish Oils
2. Caramel Color	9. Licorice

3. Carrageenan(intravenous only)	10. Periwinkle(vinca)
4. Echinacea**	11. Poria Mushroom
5. Indole-3-carbinol	Note : ** Can be immunestimulating also
6. Ipriflavone	
7. Hydrazine	

Subjects who, in the assessment by the investigator, require the use of any of the aforementioned treatments for clinical management should be removed from the trial. Subjects may receive other medications that the investigator deems to be medically necessary.

The Exclusion Criteria describes other medications which are prohibited in this trial. There are no prohibited therapies during the Post-Treatment Follow-up Phase.

7.10 Pharmacokinetic/Pharmacodynamic Evaluations

NA

7.11 Blood Collection for Anti-Pembrolizumab Antibodies

NA

7.12 Withdrawal/Discontinuation

When a subject discontinues/withdraws prior to trial completion, all applicable activities scheduled for the final trial visit should be performed at the time of discontinuation. Any adverse events which are present at the time of discontinuation/withdrawal should be followed in accordance with the safety requirements outlined in Section 9 - Assessing and Recording Adverse Events. Subjects who a) attain a CR or b) complete 24 months of treatment with pembrolizumab may discontinue treatment with the option of restarting treatment if they meet the criteria specified in Section 7.4.9. After discontinuing treatment following assessment of CR, these subjects should return to the site for a Safety Follow-up Visit (described in Section 7.4.6) and then proceed to the Follow-Up Period of the study (described in Section 7.4.7).

7.13 Blinding/Unblinding

N/A

7.14 Diet/Activity/Other Considerations

Subjects should maintain a normal diet unless modifications are required to manage an AE such as diarrhea, nausea or vomiting.

7.15 Contraception

Pembrolizumab may have adverse effects on a fetus in utero. Furthermore, it is not known if pembrolizumab has transient adverse effects on the composition of sperm. Non-pregnant, non-breast-feeding women may be enrolled if they are willing to use 2 methods of birth control or are considered highly unlikely to conceive. Highly unlikely to conceive is defined as 1) surgically sterilized, or 2) postmenopausal (a woman who is ≥ 45 years of age and has not had menses for greater than 1 year will be considered postmenopausal), or 3) not heterosexually active for the duration of the study. The two birth control methods can be either two barrier methods or a barrier method plus a hormonal method to prevent pregnancy. Subjects should

start using birth control from study Visit 1 throughout the study period up to 120 days after the last dose of study therapy.

The following are considered adequate barrier methods of contraception: diaphragm, condom (by the partner), copper intrauterine device, sponge, or spermicide. Appropriate hormonal contraceptives will include any registered and marketed contraceptive agent that contains an estrogen and/or a progestational agent (including oral, subcutaneous, intrauterine, or intramuscular agents).

Subjects should be informed that taking the study medication may involve unknown risks to the fetus (unborn baby) if pregnancy were to occur during the study. In order to participate in the study they must adhere to the contraception requirement (described above) for the duration of the study and during the follow-up period. If there is any question that a subject will not reliably comply with the requirements for contraception, that subject should not be entered into the study.

7.16 Use in Pregnancy

If a subject inadvertently becomes pregnant while on treatment with pembrolizumab, the subject will immediately be removed from the study. The site will contact the subject at least monthly and document the subject's status until the pregnancy has been completed or terminated. The outcome of the pregnancy will be reported to the Sponsor and to Merck without delay and within 24 hours to the Sponsor and within 2 working days to Merck if the outcome is a serious adverse experience (e.g., death, abortion, congenital anomaly, or other disabling or life-threatening complication to the mother or newborn).

The study investigator will make every effort to obtain permission to follow the outcome of the pregnancy and report the condition of the fetus or newborn to the Sponsor. If a male subject impregnates his female partner, the study personnel at the site must be informed immediately and the pregnancy reported to the Sponsor and to Merck.

7.17 Use in Nursing Women

It is unknown whether pembrolizumab is excreted in human milk. Since many drugs are excreted in human milk, and because of the potential for serious adverse reactions in the nursing infant, subjects who are breast-feeding are not eligible for enrollment.

8.0 TUMOR IMAGING, ASSESSMENT OF DISEASE AND BIOMARKERS

8.1 Imaging Schedule

- Clinical standard of care MRIs are done at baseline, 12 weeks post radiation and then every 9 weeks (see special instructions below for evaluating persistent radiographic progression).
- Ferumoxytol steady state MRIs and serum for biomarkers are done baseline, 12 weeks post radiation, anytime there is suspected radiographic progression and 6 weeks after suspected radiographic progression.

Imaging instructions for evaluating persistent radiographic progression: if there is suspected progression, subjects undergo a ferumoxytol steady state MRI and continue on pembrolizumab for two more cycles (total of 6 weeks). At the 6 weekpoint, clinical standard of care and ferumoxytol MRIs will be repeated to confirm persistent radiographic progression. If the 6 week scan confirms progression, then pembrolizumab is discontinued and subject is evaluated for surgery. If histopathology confirms pseudoprogression or is inconclusive, the subject will continue on pembrolizumab every 3 weeks until further radiographic progression is suspected. If histopathology confirms progression, the subject will be removed from the study.

8.2 Response assessment

8.2.1 Brain Lesions:

Complete response (CR): Complete disappearance of all enhancing abnormalities on clinical enhanced MRI scan (in the absence of gadolinium, ferumoxytol enhancement will be used). Some subjects will have a small but persistent enhancing abnormality on MRI related to biopsy or focal hemorrhage. It is often difficult to ascertain whether this represents a residual nidus of tumor or scar tissue. Adjunctive radiologic studies such as SPECT or PET as clinically indicated may be helpful, but often the nature of these abnormalities may only be determined by following the subject with serial scans. If this type of abnormality does not change or slowly involutes over time off therapy and corticosteroids, it is reasonable to categorize it as a CR.

Partial Response (PR): At least 50% decrease in the contrast enhancing lesion seen on MRI as compared to baseline imaging. In the event of multiple lesions, the determination of partial response will be based on the sum of the bi-dimensional measurements (greatest diameter x greatest perpendicular) across lesions AND no new sites of disease

Stable disease (SD): less than a PR but is not progressive disease.

Progressive disease (PD):

- **Suspected Radiographic Progression:** progression will be defined by a 20% increase in volume of enhancement compared to the best response on clinical standard of care MRI. At any time point if progression is suspected on the clinical scan, additional steady state ferumoxytol MRI will be performed within 7 days of the clinical scan. Progression will then be confirmed with a follow up scan in 4 weeks +/-5 days with a clinical standard of care MRI scan and additional ferumoxytol scan.
- **Persistent Radiographic Progression:** sustained and evident progression greater than increase in volume of enhancement compared to best response on a follow up scan at least 4 weeks after the scan where progression was suspected as per RANO BM form arm 1 or RANO criteria for subjects in arm 2. In cases with persistent radiographic progression the date of initial scan when progression was suspected will be considered to be the date of progression.
- Appearance of any new lesion or site of disease in the brain during or at the end of therapy.

- **Confirmation of true progression:** For the purpose of this study, Histopathologic evidence of viable tumor cells in patients with persistent radiographic progression will be define to have confirmed true progression. True progression is confirmed by histopathology, Pembrolizumab will be stopped and patient will be taken off-study.. Patients who refuse biopsy or biopsy is not deemed clinically necessary will be taken off study at persistent radiographic progression. However, they will be continued to be monitored with clinical MRI scan and until death.
- **Pseudoprogression (PsP):** for the purpose of this pilot study, PsP may be confirmed by imaging or by pathology.
 - PsP Imaging: stable or decrease in volume of enhancement at 4 weeks (± 5 days) after suspected radiographic progression.
 - PsP pathology: No viable tumor tissue is seen by histopathology evaluation on tissue obtained after confirmed radiographic progression by imaging.
- **Clinical progression:** Subjects may be removed from study if they experience symptomatic deterioration without radiographic evidence of disease progression.

Not evaluable (NE): Only relevant if any of the target lesions had additional interventions for clinical managements, patient is unable to get follow up scans or images are of poor quality.

Duration of Best Response: The duration of best response is measured from the time measurement criteria are met for SD, CR or PR (whichever is first recorded) until the first date that recurrent or PD is objectively documented (taking as reference for PD the smallest measurements recorded since the treatment started).

Progression free survival and overall survival will be calculated from the date of diagnosis to the date of confirmed progression or death, respectively. The date of diagnosis was used because the time between the date of diagnosis and the start of treatment or date of enrollment may vary due to subject variables or logistical issues based on radiation planning.

8.2.2 Systemic Lesions:

Measurements based on RECIST version 1.1 will be used to make a diagnosis of suspected systemic progression; it will be confirmed using irRC at follow-up.

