5.3.3 Clinical Criteria for Early Trial Termination

Early trial termination will be the result of the criteria specified below:

1. Quality or quantity of data recording is inaccurate or incomplete
2. Poor adherence to protocol and regulatory requirements
3. Incidence or severity of adverse drug reaction in this or other studies indicates a potential health hazard to subjects
4. Plans to modify or discontinue the development of the study drug

In the event of Merck decision to no longer supply study drug, ample notification will be provided so that appropriate adjustments to subject treatment can be made.

Product: Pembrolizumab

39

Protocol/Amendment No.: #7 Date: 3/31/2022

¹Brain surgery is not necessary before enrollment. However, a brain surgery may be done prior to enrollment or at the time of persistent radiographic progression if clinically indicated. Pembrolizumab needs to be stopped for 4 weeks prior to and will not be restarted for at least 4 weeks after surgery (section 7.2). All tissue will be sent for biomarkers.

²Physical exam only required with every pembrolizumab infusion.

³CBC and CMP to be done with every cycle while on pembrolizumab – labs must be done within 30 days before first pembrolizumab infusion, and within 72 hours before subsequent infusions.

⁴ FT4 and TSH with every cycle while on pembrolizumab

⁵Clinical standard of care MRIs (gadolinium with perfusion) are done at baseline, 12 weeks post radiation, then every 9 weeks, and 6 weeks after suspected radiographic progression (see special instructions below for evaluating persistent radiographic progression). All timepoints are ± 15 days. Clinical scans may be done more frequently, at physician's discretion. Each MRI scan will be evaluated for progression.

⁶Ferumoxytol steady state MRIs (within 10 days of clinical standard of care MRIs) are done baseline, 12 weeks post radiation, anytime there is suspected radiographic progression and 6 weeks after suspected radiographic progression. All timepoints are ± 15 days. Serum biomarkers will be obtained ± 15 days of ferumoxytol MRI scan.

⁷ Follow-up after completing 2 years of treatment or 32 cycles (whichever comes later): clinical standard of care MRI and clinical visit every 12 weeks ($+30$ days) for up to 1 year, and every 6 months ($+30$ days) until death.

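### Section 8.2.1 ties the imaging-pseudoprogression label to a scan at 4 weeks ±5 days, the rest of the protocol schedules that scan at about 6 weeks, and Section 10.2 does not say which defines the lesions in primary specificity

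*Combined protocol and SAP*

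**What the plan says.** Section 8.2.1 is consistent within itself on timing. After suspected progression, "Progression will then be confirmed with a follow up scan in 4 weeks +/-5 days". Pseudoprogression may be shown by imaging, as "PsP Imaging: stable or decrease in volume of enhancement at 4 weeks" with a ±5-day window, or by pathology, as "No viable tumor tissue is seen by histopathology evaluation on tissue obtained after confirmed radiographic progression by imaging". Persistent progression is judged on a later scan with a lower time limit only: "sustained and evident progression greater than increase in volume of enhancement compared to best response on a follow up scan at least 4 weeks".

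Other sections place the same confirmation scan later:

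- Schedule of Events (Section 6.0), footnote 6, for ferumoxytol MRI: "anytime there is suspected radiographic progression and 6 weeks after suspected radiographic progression. All timepoints are ± 15 days". Footnote 5 gives the same timing for the clinical MRI.
- Table 4 (Section 7.1), for ferumoxytol, and Section 7.2: 6 weeks ±15 days. Section 7.2 words the ferumoxytol scan as within that time.
- Section 8.1, directly before the definitions: "At the 6 weekpoint, clinical standard of care and ferumoxytol MRIs will be repeated to confirm persistent radiographic progression". Section 7.4.3.1 and the imaging instructions under the Schedule say the same.
- Section 2.0: 6 weeks ±5 days. Section 4.6: within 6 weeks ±5 days. Section 4.8.3.1: at least 6 weeks.

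Section 7.4 sends the reader to the Schedule of Events for test timing. Section 8.3 limits ferumoxytol imaging to the Schedule's time points.

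Section 10.2 bases primary specificity on lesions whose pseudoprogression was established by surgery or by a follow-up scan, and refers to 10.1 for detail. Neither section states when that scan is done or cites the definition in 8.2.1.

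**The concern.** The two competing labels behave differently on a 6-week scan. Persistent progression can be judged there, because its only time condition is a minimum of 4 weeks. Imaging pseudoprogression has a closed window that ends on day 33. A lesion that has stopped growing by a day-42 scan, exactly on schedule, therefore falls outside the only written definition of imaging pseudoprogression.

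That label is half of the reference standard for primary specificity. Operated lesions with a clear result are settled by histology, and Section 7.2 already leaves subjects with persistent progression and no surgery out of the primary analysis. The uncertainty therefore falls on unoperated lesions that did not progress further. If the analyst follows 8.2.1 literally, many of them may drop out of the denominator. If the analyst accepts the scheduled scan, they stay in. The plan does not say which, so the choice could be made after rCBV is known.

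**Working it through.** **1. The plan's own figure.** Section 10.1 assumes 8 subjects with pseudoprogression, half with two lesions and half with one: 4 × 2 + 4 × 1 = 12 lesions. For 10 of 12 correctly identified, the exact (Clopper-Pearson) 95% interval is 51.6% to 97.9%. This matches the 83% (52% to 98%) in Table 11, and the other four rows also reproduce.

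**2. The windows in days after suspected progression.** The 4-week window is 28 ± 5 = days 23-33, which is 11 days.

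| Source | Timing | Days | Shared with days 23-33 |
|---|---|---|---|
| Schedule footnotes 5 and 6, Table 4, Section 7.2 (clinical MRI) | 6 weeks ±15 days | 42 ± 15 = 27-57 | 27-33: 7 of the 11 days (7 of the Schedule's 31) |
| Section 2.0 | 6 weeks ±5 days | 42 ± 5 = 37-47 | none |
| Sections 7.4.3.1 and 8.1, imaging instructions under the Schedule | 6 weeks | 42 | none |
| Section 4.8.3.1 | at least 6 weeks | 42 onward | none |
| Section 4.6; Section 7.2 (ferumoxytol MRI) | within 6 weeks, ±5 or ±15 days | upper limit only, if read as a maximum | possible |

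The nominal day 42 lies 42 − 33 = 9 days past the end of the 4-week window. Of the Schedule's 31 permitted days, 31 − 7 = 24 fall outside it.

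**3. How many specificity lesions rest on the imaging label.** Inputs from Section 10.1: 15 subjects operated, 12 of them with true progression, typically one lesion operated per subject, 12 pseudoprogression lesions.

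- Operated subjects without true progression: 15 − 12 = 3.
- If each contributes one pseudoprogression lesion: 3 lesions labelled by surgery, 12 − 3 = 9 by imaging (9/12 = 75%).
- If only 2, 1 or none of the 3 does so: 10, 11 or 12 by imaging.
- If two lesions are operated in each of the 3: 12 − 6 = 6 by imaging (50%).

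So the figure is about 9 of 12, with a range of 6 to 12. It assumes one operation per subject; repeat surgery could lower it.

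**The case against.** Scan timing is less open than a list of conflicting passages suggests. Sections 7.4 and 8.3 defer to the Schedule of Events, and its ±15-day window covers 7 of the 11 days in the 4-week window. Extra clinical scans are allowed, so some lesions will have one in days 23-33. Section 7.2 already treats a lesion that is unchanged or smaller at 6 weeks as not persistent. All of this stands, and it narrows the problem to a label definition that does not match the schedule. It does not remove it: the nominal scan day still lies outside the definition, and the Section 7.2 rule governs treatment, does not name pseudoprogression and is not cited in 10.2.

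Three stronger readings are tempting, but the documents do not support them.

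- A reader might infer that specificity would shrink to the few surgically labelled lesions. That requires every follow-up scan to miss days 23-33 and the analyst to apply 8.2.1 literally, whereas 10.2 accepts a follow-up scan without a window. No rate of label change is given, so no expected effect can be calculated.
- A reader might infer that one lesion can meet both labels, having grown and then stabilised while still above best response. That depends on the threshold for persistence. None is readable in the text, and a number may have been lost from the PDF. If stable is read through "Stable disease (SD): less than a PR but is not progressive disease", the overlap disappears.
- A reader might take 9 of 12 as the plan's own statement. It is derived. Section 10.1 does not say that the 3 remaining operated subjects have pseudoprogression, and Section 8.1 foresees inconclusive histology.

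**Conclusion.** The contradiction is in the current text, and the rule misfires as written: imaging pseudoprogression is defined on days 23-33, while the scan meant to show it is scheduled around day 42. It reaches the primary endpoint because about 9 of the 12 planned specificity lesions (6 to 12, under the assumptions above) would take their reference label from imaging, and Sections 10.1 and 10.2 do not settle the timing. The study is descriptive and not powered for a formal hypothesis, so the consequence is a specificity whose denominator is poorly defined, not an invalid test. The size of any shift in the estimate cannot be derived from the documents. Nothing here says which interval is right.

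**What to change.** **Protocol.** Reconcile Sections 2.0, 4.6, 4.8.3.1, the Schedule of Events footnotes and imaging instructions, Table 4, and Sections 7.2, 7.4.3.1, 8.1 and 8.2.1 to one confirmation interval and window. The choice is the sponsor's, because the same scan leads to decisions on stopping treatment and on surgical evaluation. Align the pseudoprogression and persistence definitions in 8.2.1 to that scan and to the same reference volume. Correct the phrase "as per RANO BM form arm 1 or RANO criteria for subjects in arm 2", since Section 1.0 lists no treatment groups.

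**Section 10.2.** Cross-refer to the reconciled definition and state that the imaging label comes from the confirmation scan under that rule. Record the day of the scan. Require the label to be assigned without knowledge of rCBV; the reader blinding in 8.4.1 covers map type and subject information and does not address this. Report how many specificity lesions were labelled by surgery and how many by imaging. A sensitivity analysis over the superseded wordings is not needed: read literally, the 4-week wording would reject most 6-week imaging labels, so it would mainly reproduce the discarded rule.

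**Cost.** Wording changes, one sponsor decision and slightly more reporting. No new scans are needed.

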2.1 Trial Diagram

3.0 OBJECTIVES & RATIONALE

Primary Objective

1. Determine the sensitivity and specificity of relative cerebral blood volume (rCBV) measured by steady state MRI with ferumoxytol in predicting true vs pseudoprogression after SRS and intravenous (IV) pembrolizumab in subjects with brain metastases from NSCLC.

Rationale: This study is not powered to test any formal hypothesis and we aim to collect preliminary data on the sensitivity and specificity of rCBV measurements with ferumoxytol in the primary objective.

Secondary Objectives

1. Evaluate the safety and tolerability of pembrolizumab when given with SRS in subjects with brain metastasis.
2. Evaluate progression free survival, overall survival, best response in brain disease, best response in systemic disease, and duration of best responses of brain and systematic diseases.

Rationale: Given the small sample size, we aim to collect preliminary data on survival, safety, tolerability and efficacy of pembrolizumab when given with SRS in subjects with brain metastasis. No additional toxicity profile is expected when pembrolizumab is used in combination with SRS and ferumoxytol. Toxicities will be evaluated using CTCAE version

4.0. Subjects will have ongoing toxicity evaluation, with documentation of infusion related reactions (grade 3, 4), hematologic toxicities (grade 3, 4) and all other grade 3, 4 toxicities. Each toxicity will be attributed to pembrolizumab and ferumoxytol or neither/both.

Exploratory Objectives

1. Compare the immune response as determined by the volume, pattern and intensity of delayed (24hr) ferumoxytol uptake between subjects who develop true vs pseudoprogression.
2. Investigate the serum immunological parameters and correlate clinical as well as radiological response with systemic immune response to pembrolizumab as measured by immunological panel.
3. Compare the changes percentage expression in PDL-1 in the biopsy tissue before and after therapy at the time of progression.
4. In subjects with measurable systemic lesions, investigate the feasibility of measuring vascular volume fraction (VVF), vessel size index (VSI) and vessel density index (VDI) as surrogate for response (true vs. pseudoprogression, as measured with RECIST 1.1 criteria).

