7.2 Study procedures narrative

Enrolled subjects will receive pembrolizumab (200 mg I.V. every 3 weeks) starting on the first day of radiation (\pm 15 days) until persistent radiographic progression is confirmed. [Subjects may receive standard of care cytotoxic chemotherapy \(carboplatin and pemetrexed\) while on trial, at the treating physician's discretion.](#) [72, 73] MRI scans will be performed to assess response to therapy. Clinical standard of care MRIs are done at baseline, 12 weeks post radiation and then every 9 weeks thereafter until suspected radiographic progression. An early follow up clinical standard of care MRI will be performed 6 weeks (\pm 15 days) from the date of MRI showing suspected radiographic progression to confirm persistent radiographic progression. Clinical scans may be done more frequently, based on physician's discretion. Each MRI scan will be evaluated for progression.

Additional ferumoxytol steady state MRIs will be done at baseline, 12 weeks after radiation, at suspected radiographic progression and within 6 weeks (\pm 15 days) from suspected radiographic progression to confirm persistent radiographic progression.

When persistent radiographic progression is confirmed, subjects will be evaluated for a craniotomy with intent to complete resection and /or biopsy of the enhancing lesion, if this is thought to be the clinical standard of care.

Biopsy tissue obtained from surgery at persistent radiographic progression will be evaluated by the pathologists at OHSU. The pathologist will determine if the tissue is consistent with progression or pseudoprogression, where progression is defined as presence of viable metastatic carcinoma in the biopsy tissue and absence of tumor cell is assumed to reflect pseudoprogression. If histopathology confirms pseudoprogression the subject will continue on pembrolizumab every 3 weeks until further radiographic progression is suspected. If histopathology confirms progression, the subject will be removed from the study, followed clinically with serial clinical stand of care MRIs every 3 months for up to a year and then every 6 months until death or lost to follow-up.

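### Duration of best response in the brain starts at the first record of SD, CR or PR, so a late responder's stable-disease time is counted as response time

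*Combined protocol and SAP*

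**What the plan says.** Section 3.0 lists, among the secondary objectives, "duration of best responses of brain and systematic diseases". Section 8.2.1 gives the rule for the brain: "The duration of best response is measured from the time measurement criteria are met for SD, CR or PR (whichever is first recorded". The clock stops when recurrence or PD is first objectively documented, "taking as reference for PD the smallest measurements recorded since the treatment started".

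The same section defines SD as "less than a PR but is not progressive disease", while PR requires enhancement to fall by at least half from baseline. When progression persists on the follow-up scan, "the date of initial scan when progression was suspected will be considered to be the date of progression".

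Section 7.2 schedules clinical brain MRI at baseline, "12 weeks post radiation and then every 9 weeks thereafter until suspected radiographic progression". Footnote 5 of the Schedule of Events (Section 6.0) adds "All timepoints are ± 15 days" and "Clinical scans may be done more frequently" at the physician's discretion.

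The analysis plan gives no other start date. Sections 10.0 and 10.2 summarise the distribution of best responses with proportions and exact confidence intervals, and name Kaplan-Meier only for progression free and overall survival. Section 8.2.2 has no duration rule for systemic lesions, so the point concerns the brain only.

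**The concern.** Because SD covers everything between PR and PD, any evaluable subject without PD at the first follow-up scan starts the clock at that scan, whether or not a response has occurred. If CR or PR comes later, the start date says nothing about when the response began. The end date can still depend on the response, since PD is judged against the smallest measurement so far. For a subject who is SD first and CR or PR later, the quantity is nearer to duration of disease control than to duration of best response.

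The protocol itself expects this sequence. Section 4.4 says responses to immunotherapy may be slow or delayed, and Section 4.8.3.1 says benefit can take months to appear. An early responder, a late responder and a subject who was never more than stable can all end with the same recorded duration. A summary over such subjects does not show how long responses lasted, and Section 4.8.3.1 intends the pilot's data to inform a larger study.

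**Working it through.** The documents state no figure for this endpoint, so there is none to reproduce. The check applies the rule to the nominal scan schedule.

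**Inputs**
- Scans at weeks 12, 21, 30, 39, 48 and so on after radiation (Sections 7.2 and 8.1).
- Start and end of the clock, and the definition of SD (Section 8.2.1).
- Window of ±15 days (Section 6.0, footnote 5).
- Assumption: PD is first documented at week 48 = 12 + 4 × 9. This is illustrative and not in the documents. Under Section 8.2.1 it is the date of the scan that first raised suspicion, once progression is confirmed.
- Assumption: no suspected progression before the first CR or PR, because Section 7.2 states the 9-week schedule only up to that point.

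**Excess**

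Duration under the rule = PD week − week of first SD, CR or PR.

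Duration of response = PD week − week of first CR or PR.

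The PD date cancels, so the excess = week of first CR or PR − week of first SD record.

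| First CR/PR (SD at earlier scans) | Excess, weeks | Rule, PD at week 48 | From first CR/PR | Ratio |
|---|---|---|---|---|
| Week 12 | 12 − 12 = 0 | 48 − 12 = 36 | 48 − 12 = 36 | 1.0 |
| Week 21 | 21 − 12 = 9 | 36 | 48 − 21 = 27 | 1.3 |
| Week 30 | 30 − 12 = 18 | 36 | 48 − 30 = 18 | 2.0 |
| Week 39 | 39 − 12 = 27 | 36 | 48 − 39 = 9 | 4.0 |
| Never (SD only) | not applicable | 36 | no response | not applicable |

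**Dependence on the PD date.** The excess in weeks is the same whatever PD date is assumed; the ratio is not. For a first response at week 39, PD at week 57 gives (57 − 12)/(57 − 39) = 45/18 = 2.5, and PD at week 75 gives (75 − 12)/(75 − 39) = 63/36 = 1.75.

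**Scan windows.** The documents do not say how the ±15 days apply. If the interval runs from the previous scan, 15 days = 2.14 weeks and the 9-week excess spans 9 ± 2.14, or 6.9 to 11.1 weeks. If both scans have windows around fixed dates, 30 days = 4.29 weeks and it spans 9 ± 4.29, or 4.7 to 13.3 weeks. Discretionary scans would also shift these values.

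**The case against.** The best defence is that the endpoint is duration of *best* response, not of objective response. SD is a defined category and can be a subject's best response, so it belongs among the start events. That is right for subjects whose best response is SD, and the fix keeps their clock. It does not justify starting at SD for a subject whose best response is CR or PR.

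The sentence might also be meant as the first record of the subject's own best category. The wording does not say that, and nothing elsewhere supports it. If that was the intent, the text still needs correcting, because read literally it gives different dates.

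Three further points stand and limit the finding:
- This is a 20-subject descriptive pilot, and no decision rule or sample size depends on this duration.
- Subjects already in CR or PR at the first follow-up scan have no excess. Tabulating durations by best-response category would separate the SD-only subjects, though not early from late responders.
- The ratios depend on an assumed PD date, and 4.0 is the most extreme case in the table. The excess in weeks is the firmer measure.

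Duration from first CR or PR could be derived later from the dated scans, but it would then not be prespecified.

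**Conclusion.** The concern holds. As written, the rule counts stable time as response time for every subject whose best brain response is CR or PR but who was first recorded as SD. The excess is 9 weeks per scheduled scan interval between the first SD record and the first CR or PR, so 9, 18 or 27 weeks for a response first seen at week 21, 30 or 39, and zero for one seen at week 12.

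These values assume the nominal schedule and no suspected progression before the response. The documents do not give the proportion of responders who would be SD first, so the average effect cannot be stated. The primary endpoint and the sample size are unaffected. The change should be made because a named secondary objective is measured by a rule that does not match its label for this subgroup.

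**What to change.** In Section 8.2.1, split the definition by best response:
- Best response CR or PR: start at the first scan meeting CR or PR; end at documented recurrence or PD, as now.
- Best response SD: report separately as duration of stable disease, from the first SD record to PD, as now.

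The text should state that the first measure runs from the first of CR or PR, so a subject who passes through PR on the way to CR has the PR time included.

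The change uses scans that are already dated and needs no new visits or subjects. The cost is that reported durations become shorter for late responders and 20 subjects are divided into two smaller groups. Relabelling the present measure as duration of disease control would be cheaper still, but would leave the duration of CR and PR unreported.
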